12.2. Analysis Set

12.2.1. Screened Set

The screened set will include all participants who provide written informed consent. This set will be used only for the purpose of describing participant disposition.

12.2.2. Safety Set

The safety set will include all participants who receive at least 1 dose of study drug in the RCP. Participants will be analyzed according to the treatment they received.

12.2.3. Intent-to-Treat Set

The intent-to-treat (ITT) set will include all randomized participants. Participants will be analyzed according to their assigned treatment, regardless of the treatment actually received. All efficacy analyses will be performed with the ITT set.

12.2.4. Per-Protocol Set

The per-protocol (PP) set will include all participants in the ITT set who have not violated any inclusion or exclusion criteria and/or deviated from the protocol in a way that could influence their efficacy assessment. Decisions concerning the exclusion of participants from the PP analysis set will be made and documented prior to database lock.

12.2.5. Pharmacokinetic Set

The PK set will include all participants in the ITT set who receive pegcetacoplan and have at least 1 evaluable postdose PK measurement.

12.2.6. Pharmacodynamic Set

The PD set will include all participants in the ITT set who receive pegcetacoplan and have at least 1 evaluable postdose PD measurement.

12.2.7. Data Review for Analysis Set

After all the data have been verified, coded, and entered into the database, a review will be performed to check the quality of the data, identify any outliers, and make decisions on how to deal with any data issues (eg, missing values, withdrawals, protocol deviations). After this review, resolution of all issues, and documentation of all decisions, the database will be locked.

12.3. Efficacy Analysis

12.3.1. Analysis of Primary Efficacy Endpoint

The targeted treatment regimen to be used for this study is pegcetacoplan or placebo plus stable regimen for C3G/IC-MPGN treatment. The primary estimand on the treatment effect of pegcetacoplan is for the participant population as defined through the study inclusion/exclusion criteria, with the primary endpoint based on the log-transformed ratio of uPCR (sampled from first-morning urine collections) at week 26 compared to baseline using an equal-weighted average over weeks 24, 25, and 26.

Population level summary is the treatment difference in the mean change from baseline in log-transformed ratio to baseline in uPCR of pegcetacoplan over placebo.

A hypothetical strategy will be used for addressing the intercurrent events (ICEs) that are listed in ICE categories 1 and 2 in Table 8. In the hypothetical strategy, uPCR data collected at visits after the occurrence of ICEs will be set as missing and will be imputed using different approaches as described in Table 8. A treatment policy strategy will be used for ICEs of premature discontinuation of treatment (ICE category 3). In the treatment policy strategy, any measured value will be used as is.

The primary endpoint will be analyzed using a mixed effect model for repeated measures (MMRM). The model will include fixed categorical effects for treatment group, visit, disease type (C3G vs IC-MPGN), stratification factors, and the visit-by-treatment group interaction, as well as the continuous, fixed covariate of baseline log-transformed uPCR. Initially, an unstructured covariance matrix will be investigated. If this analysis fails to converge, other covariance structures will be used; details will be provided in the statistical analysis plan. The difference between treatment groups using a composite contrast of equal-weighted average over weeks 24, 25, and 26 will be estimated with its 95% CI and corresponding *P* value. The model will be applied to each multiply imputed data set, and results from each imputed data set will be combined using Rubin's rule (Rubin 1976).

The primary efficacy analysis will be conducted using the ITT set. Supplemental analysis based on alternative estimands, analysis using the PP set, and sensitivity analyses for assessing the robustness of the primary analysis results will be performed and prespecified in the SAP.

Subgroup analyses will also be conducted to describe findings within both stratification factors in addition to other important prognostic factors such as disease type, age, sex, baseline uPCR, etc.

Table 8: Intercurrent Events During the Randomized Treatment Phase and Strategies Addressing Intercurrent Events for the Primary Efficacy Endpoint

ICEs	Strategies for addressing ICEs
ICE Category 1 Use of prohibited concomitant medication in the protocol (Section 8.3.3) Use of rescue therapies defined in the protocol (Section 8.3.2)	Hypothetical strategy will be used where all measurements after events under any ICE in this category will be set to missing. Missing data resulting from these ICEs will be imputed using reference-based imputation.
ICE Category 2 Start renal replacement therapy (dialysis)	Hypothetical strategy will be used where all measurements after the ICEs will be set as missing. Missing data resulting from these ICEs will be imputed based on the worst change of all participants across visits plus a random error.
ICE Category 3 Permanent discontinuation of study treatment.	Treatment policy strategy will be used whereby any measured value will be used as is. Missing data resulting from the ICEs will be imputed using reference-based imputation.

Abbreviations: ICE = intercurrent event.

12.3.2. Analysis of Secondary Efficacy Endpoints

To preserve the overall type I error among the primary endpoint and key and additional secondary endpoints, a fixed-sequence testing strategy will be used; hence, statistical significance of the first secondary endpoint will be evaluated only if statistical significance is achieved with the primary analysis of the primary endpoint. The remaining secondary endpoints will also adhere to this testing strategy, and their order will match the order in which they are presented in Section 5.2.1.

12.3.2.1. Key Secondary Efficacy Endpoints:

• The numbers and proportion of participants who meet the criteria for achieving a composite renal endpoint at week 26 will be tabulated by treatment group and analyzed using a logistic regression model with treatment group as the independent variable and adjusted for baseline eGFR values, baseline log-transformed uPCR values, disease type, and stratification factors. The *P* value and odds ratio of being a responder for the pegcetacoplan group to being a responder for the placebo group with associated 95% CI will be provided.

A participant meets the requirements of the composite renal endpoint if he/she satisfies: (1) a stable or improved eGFR compared to baseline (\leq 15% reduction in eGFR), and (2) a \geq 50% reduction in uPCR compared to baseline.

A composite strategy will be used for addressing the ICEs listed in Table 9. In the composite strategy, the composite renal endpoint status at or after the occurrence of any of these ICEs below will be regarded as non-responder.

Table 9: Intercurrent Events During the Randomized Treatment Phase and Strategies Addressing Intercurrent Events for the Composite Renal Endpoint

ICEs	Strategies for addressing ICEs
Use of prohibited concomitant medication in the protocol (Section 8.3.3)	Composite strategy. The composite renal endpoint status at or after the initiation of any of ICEs will be regarded as
Start renal replacement therapy (dialysis)	non-responder.
Use of rescue therapies defined in the protocol (Section 8.3.2)	
Permanent discontinuation of study treatment	

Abbreviations: ICE = intercurrent event.

• The numbers and proportion of participants who achieve uPCR response at week 26 will be tabulated by treatment group and compared using a logistic regression model with treatment group as the independent variable and adjusted for baseline uPCR values, disease type, and stratification factors. The *P* value and odds ratio of being a responder for the pegcetacoplan group to being a responder for the placebo group with associated 95% CI will be provided. ICEs will be handled as described in Table 9.

The uPCR response, defined as a reduction of at least 50% from baseline in uPCR at week 26, will be calculated using the following steps:

- 1. Baseline uPCR value will be calculated as the average of the uPCR measurements from at least 6 of the 9 FMU samples collected between the start of screening and day 1, inclusive. The uPCR values used to calculate baseline should include those from the samples collected on day -2, day -1, and before dosing on day 1.
- 2. Week 26 uPCR value will be calculated as the average of the uPCR measurements from at least 6 of the 9 FMU samples collected in week 24, week 25, and week 26.
- 3. Each participant will be categorized as either a success or a failure according to whether the change from baseline in uPCR calculated from steps 1 and 2 is a reduction of at least 50%.

For participants with evaluable renal biopsies, evaluation of the change from baseline to week 26 in the C3G histologic index activity score will use an analysis of covariance (ANCOVA) model with treatment as a fixed effect, adjusted for baseline C3G histologic index activity score, disease type, and stratification factors. Least-square (LS) means will be presented for each treatment group, along with the between-treatment difference, 95% confidence interval, and *P* value. The strategies to handle intercurrent events are the same as those for the primary endpoint. This endpoint will be evaluated based on adult participants only because neither the week 26 renal biopsy nor an on-study baseline renal biopsy are required for adolescent participants. All data, including any data from adolescent participants, will be included in a summary table.

For participants with evaluable renal biopsies, the numbers and proportion of participants showing decreases in C3c staining intensity of at least 2 orders of magnitude from baseline to the week 26 renal biopsy will be tabulated by treatment group and compared using a logistic regression model with treatment group as the independent variable and adjusted for baseline C3c staining, disease type, and stratification factors. The odds ratio of being a responder for the pegcetacoplan group to being a responder for the placebo group and associated 95% CI and *P* value will be provided. ICE will be handled the same as Table 9. This endpoint will be evaluated based on adult participants only because neither the week 26 renal biopsy nor an on-study baseline renal biopsy are required for adolescent participants.

• Change from baseline in eGFR at week 26 will be tabulated by treatment group and analyzed using a MMRM model. The model will include fixed categorical effects for treatment group, visit, disease type, stratification factors, and the visit-by-treatment group interaction, as well as the continuous, fixed covariate of baseline eGFR values. Initially, an unstructured covariance matrix will be investigated, if this analysis fails to converge, other covariance structures will be used, details will be provided in the statistical analysis plan. The difference between treatment groups will be estimated with its 95% CI and corresponding *P* value. The strategies to handle intercurrent events are similar to those for the primary endpoint.

12.3.2.2. Additional Secondary Efficacy Endpoints:

- The proportion of participants achieving proteinuria <1 g/d at week 26 will be analyzed using the same approach as the first key secondary endpoint.
- For participants with serum albumin levels below the LLN at baseline, the number and proportion of participants with normalization of serum albumin at week 26 will be calculated using the following steps:
 - 1. Baseline serum albumin value will be calculated as the average of up to 2 serum albumin measurements preceding and including day 1. Participants will be included in the denominator of this calculation only if the baseline albumin value is below the LLN.
 - 2. Week 26 serum albumin values will be calculated as the average of up to 2 serum albumin measurements preceding and including week 26.
 - 3. Each participant will be categorized as either a success or a failure according to the week 26 serum albumin values as calculated in Step 2. Values greater than or equal to the LLN will be categorized as a success; values less than the LLN will be categorized as a failure.

For participants with serum albumin levels below the LLN at baseline, the numbers and proportion of participants with normalization of serum albumin at week 26 will be tabulated by treatment group and compared using a logistic regression model with treatment group as an independent variable and adjusted for baseline albumin value, disease type, and stratification factors. The *P* value and odds ratio of showing serum albumin above the LLN at week 26 for the pegcetacoplan group vs. the placebo group and associated 95% CI will be provided. The strategies to handle intercurrent events are the same as those for the first key secondary endpoint.

- For participants with low serum C3 levels at baseline, the number and proportion of participants with normalization of serum C3 levels at week 26 will be calculated using the following steps:
 - 1. Baseline serum C3 value will be calculated as the average of up to 2 serum C3 measurements preceding and including day 1. Participants will only be included in the denominator of this calculation if the baseline C3 value is below the LLN.
 - 2. Week 26 serum C3 value will be calculated as the average of up to 2 serum C3 measurements preceding and including week 26.
 - 3. Each participant will be categorized as either a success or a failure based on the week 26 serum C3 value as calculated in Step 2. Values greater than or equal to the LLN will be categorized as a success; values less than the LLN will be categorized as a failure.

For participants with low serum C3 levels at baseline, the numbers and proportion of participants with normalization of serum C3 levels at week 26 will be tabulated by treatment group and compared using a logistic regression model adjusting for baseline serum C3 level, disease type, and stratification factors. The odds ratio of showing a serum C3 level above the LLN at week 26 for the pegcetacoplan group vs. the placebo group and associated 95% CI and *P* value will be provided. The strategies to handle intercurrent events are the same as those for the first key secondary endpoint.

- The change from baseline in FACIT-Fatigue score at week 26 will be analyzed using analysis of covariance (ANCOVA) model with treatment as a fixed effect, adjusted for baseline FACIT-Fatigue score, disease type, and stratification factors. LS means will be presented for each treatment group, along with the between-treatment difference and 95% confidence interval. The strategies to handle intercurrent events are the same as those for the primary endpoint.
- The change from baseline in KDQOL score at week 26 will be analyzed using analysis of covariance (ANCOVA) model with treatment as a fixed effect, adjusted for baseline KDQOL score, disease type, and stratification factors. LS means will be presented for each treatment group, along with the between-treatment difference and 95% confidence interval. The strategies to handle intercurrent events are the same as those for the primary endpoint.

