In brief, the first urine (on the day of collection) must be discarded (as this is urine made prior to the start of the collection date/time). The time and date of this discarded void must be recorded, as it represents the start of the collection. The participant should then collect all urine over the next 24 hours. At the 24-hour time point, the participant should empty their bladder and collect this urine as the final void of the 24-hour urine collection. The date and time of this last collected void should be recorded, as it represents the end of the 24-hour urine collection.

There will be six 24-hour urine collections, at the visits outlined in the schedule of activities (Table 2):

- screening (between week –8 and week –4 and before the renal biopsy)
- week 12
- week 24 (before the week 26 renal biopsy)
- week 36
- week 48 (before the week 52 renal biopsy, if performed)
- week 60

If menses are occurring at the scheduled time of a 24-hour urine collection, then the collection should be delayed until completion of menses, with this information recorded in the participant's source document. Urine must be stored at 2 to 8 °C (ie, in refrigerator). Courier arrangements can be made by the site to pick up the collection container from the participant's home and return it to the site, or the participant may return it directly to the site. Total urine volume, total protein concentration, total albumin concentration, total β -2 microglobulin, and total creatinine concentration will be measured on the 24-hour urine collections, with calculation of total protein excretion, total albumin excretion, total creatinine excretion, total β -2 microglobulin excretion, uPCR, urinary albumin-to-creatinine ratio (uACR), and urinary β 2-microglobulin—to-creatinine ratio (uBCR) based on the 24-hour collection.

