2.2.3. Additional Secondary Efficacy Endpoints

The additional secondary endpoints are (to be evaluated at week 26):

- The proportion of participants achieving proteinuria <1 g/day
- For participants with serum albumin levels below the lower limit of normal (LLN) at baseline, the proportion of participants with normalization of serum albumin levels
- For participants with serum C3 levels below the LLN at baseline, the proportion of participants with serum C3 levels above the LLN
- The change from baseline in Functional Assessment of Chronic Illness Therapy (FACIT)—Fatigue Scale score
- The change from baseline in Kidney Disease Quality of Life (KDQOL) score

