6.4. Analyses of Primary Efficacy Endpoint

The primary efficacy endpoint is the log-transformed ratio of uPCR at week 26 compared to baseline. The null $(H_{1,0})$ and alternative $(H_{1,1})$ hypotheses for the primary efficacy analysis are:

- H_{1,0}: There is no difference in log-transformed ratio of uPCR at week 26 compared to baseline between the pegcetacoplan and placebo treatment groups.
- H_{1,1}: There is a difference in log-transformed ratio of uPCR at week 26 compared to baseline between the pegcetacoplan and placebo treatment groups.

uPCR values are expected to be highly skewed so that the values will be natural log-transformed in analysis and presentation. For the primary efficacy endpoint, sensitivity analyses (Section 6.4.2), supplemental analyses (Section 6.4.3), and subgroup analyses (Section 6.4.4) will be performed.

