6.6.1. The Proportion of Participants Achieving Proteinuria <1 g/day

The additional secondary efficacy endpoint of the proportion of participants achieving proteinuria <1 g/day (assessed by 24-hour urine protein) at week 24 will be examined with the following null ($H_{7,0}$) and alternative ($H_{7,1}$) hypotheses:

- H_{7,0}: There is no difference in proportion of participants who achieve proteinuria <1 g/day at week 24 between the pegcetacoplan and placebo treatment groups.
- H_{7,1}: There is a difference in proportion of participants who achieve proteinuria <1 g/day at week 24 between the pegcetacoplan and placebo treatment groups.

The additional secondary endpoint will be analyzed in the ITT set with participants grouped according to the treatment assigned at randomization.

A logistic model will be used to analyze the additional secondary endpoint. The model will include treatment group as the independent variable and adjusted for baseline proteinuria values, disease type (C3G vs IC-MPGN), and stratification factors. Further details on the presentation of the results are described in Section 6.1. Strategies for addressing ICEs are the same as the ones described in Section 6.5.1.1.

The numbers and proportion of participants achieving proteinuria <1 g/day at week 24 will be tabulated by treatment group.

All 24-hour urine protein data will be listed for the ITT set.

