ICE strategies will be the same as the main SAP where the endpoint status at or after the initiation of ICEs will be regarded as non-responder.

6.7.9. The Proportion of Participants with Serum C3 Levels above the LLN at Week 52

The descriptive analysis described in Section 6.6.3 in the main SAP will be repeated at Week 52 based on the ITT Set by using available data through the Week 52 assessment.

ICE strategies will be the same as the main SAP where the endpoint status at or after the initiation of ICEs will be regarded as non-responder.

6.7.10. Change from Baseline in FACIT-Fatigue Scale Score at Week 52

The descriptive analysis described in Section 6.6.4 in the main SAP will be repeated at Week 52 based on the ITT Set by using available data through the Week 52 assessment.

6.7.11. Change from Baseline in KDQOL Score at Week 52

The descriptive analysis described in Section 6.6.5 in the main SAP will be repeated at Week 52 based on the ITT Set by using available data through the Week 52 assessment.

6.7.12. The Change from Baseline in uPCR Using the 24-hour Urine Collections at Week 48

The descriptive analysis described in Section 6.7.1 in the main SAP will be repeated at Week 48 using all available data through the Week 48 assessment based on the ITT Set.

Note for the MMRM modeling for the RCP period, the analysis based on log-transformed 24-hour uPCR will be implemented, instead of the uPCR values on original scale.

6.7.13. The Annual Rate of Change from up to 3 Years Prior to Screening in eGFR

The analysis described in Section 6.7.2 in the main SAP will be repeated at Week 52 using all available data through the Week 52 assessment, with the adjustment that for the placebo group, eGFR data collected during the RCP period will be considered as part of the historical (a.k.a. pre-treatment) data in the analysis. This analysis will be based on the ITT Set.

In addition, the above analysis will be repeated by pooling the two treatment regimens and difference between post-peg and pre-peg will be presented with the 95% CI and p-value.

6.7.14. The Proportion of Participants with Reductions from Baseline in Proteinuria of at least 30% at Week 52

The descriptive analysis described in Section 6.7.3 in the main SAP will be repeated at Week 52 based on the ITT Set by using available data through the Week 52 assessment.

6.7.15. The Proportion of participants with Normalization of Proteinuria at Week 52

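### The week 24 test of proteinuria <1 g/day adjusts for what reads as one raw 24-hour baseline; logging it and adding baseline log FMU uPCR is a small gain from existing data, and the week 24/26 wording needs reconciling

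*Protocol*

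**What the plan says.** **Time point.** Protocol 12.3.2.2 states: "The proportion of participants achieving proteinuria <1 g/d at week 26 will be analyzed using the same approach as the first key secondary endpoint". SAP 2.2.3 keeps the same timing: "The additional secondary endpoints are (to be evaluated at week 26". Protocol 10.2 sets the urine schedule: "There will be six 24-hour urine collections, at the visits outlined in the schedule of activities (Table 2". These are screening and weeks 12, 24, 36, 48 and 60; the last one in the randomized period is listed as "week 24 (before the week 26 renal biopsy". SAP Table 1 and SAP 6.6.1 define the endpoint by 24-hour urine protein at week 24. Protocol Table 1 has a footnote on weeks 24 and 48, but attaches it only to the exploratory 24-hour uPCR row.

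**Model.** The first key secondary endpoint, whose approach the protocol borrows, is "adjusted for baseline eGFR values, baseline log-transformed uPCR values, disease type, and stratification factors". SAP 6.6.1 is instead "adjusted for baseline proteinuria values, disease type (C3G vs IC-MPGN), and stratification factors". It does not mention a log transform, FMU uPCR or eGFR.

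**Scale elsewhere.** SAP 6.4 says "uPCR values are expected to be highly skewed". SAP 6.5.1.1, 6.5.2.1, 6.7.3 and 6.7.4 all use log-transformed baseline uPCR in proteinuria responder models. SAP Addendum 6.7.12 later changed the 24-hour uPCR model for the randomized period: "the analysis based on log-transformed 24-hour uPCR will be implemented".

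**Declaration.** SAP 15 gives changes from the protocol as not applicable.

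**The concern.** The endpoint is measured once per participant near the end of the randomized period, so the baseline covariate is the main source of precision beyond the treatment comparison itself. The plan appears to use one 24-hour collection on a skewed scale. The baseline log FMU uPCR, normally a mean of 6 to 9 samples, is already derived for the primary analysis and is left out.

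This is the seventh of eleven tests: the primary, five key secondaries, then this one. It gates albumin, C3, FACIT-Fatigue and KDQOL. A test in the sequence should have one stated time point and one stated covariate set. A modest gain in its power also helps the four tests behind it.

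**Working it through.** **The plan's own figure.** Inputs from Protocol 12.1 and SAP 3.4: mean log ratios −0.92 and −0.22 (difference 0.70), SD 0.88, one-sided 0.025, 90% power.

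n per arm = 2 × (1.960 + 1.282)² × 0.88² / 0.70² = 33.2, so 34 per arm and 68 in total. At 35 per arm, power is 91.4% (normal) or 90.7% (noncentral t). Attrition: 70 / 0.90 = 77.8, so 78. The stated 70 and 78 reproduce, but they concern the primary endpoint. Neither document gives a responder rate or power for <1 g/day.

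**Place in the sequence.** 1 + 5 + 1 = 7, matching the hypothesis numbering in SAP 6.6.1.

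**Simulation, first set.** Logistic regression, Wald test, two-sided 0.05, 1,000 trials per cell, N = 78, 100 and 124. Log changes and SD come from the documents. Assumed: baseline median 3 g/day, log SD 0.6, 8% counted as non-responders for missing data or intercurrent events, and the error SDs below. Spread means between-patient log SD between g/day and uPCR. Disease type and strata were left out of all models alike. Responder rates were about 38% and 17%. As a rough check, 0.92 × Φ((0.92 − 1.099)/1.065) = 40% and 0.92 × Φ((0.22 − 1.099)/1.065) = 19%, with 1.065 = √(0.6² + 0.88²), ignoring measurement error and the entry cut.

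Power (%) at N = 124:

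| Setting: 24-h error, FMU error, spread | Raw 24-h (SAP as read) | Log 24-h | Log FMU + eGFR (protocol) | Log 24-h + log FMU + eGFR |
|---|---|---|---|---|
| A: 0.2, 0.1, 0 | 79.4 | 80.6 | 80.1 | 80.4 |
| B: 0.3, 0.15, 0.3 | 76.7 | 77.7 | 76.1 | 77.4 |
| C: 0.2, 0.2, 0.4 | 78.2 | 78.4 | 77.1 | 78.5 |
| D: 0.5, 0.1, 0 | 68.0 | 68.7 | 71.0 | 71.4 |
| E: as B, eGFR prognostic | 76.4 | 76.7 | 81.1 | 80.9 |

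Differences from the raw 24-hour model over all three N, in percentage points:
- Log 24-hour alone: −0.5 to +1.8.
- Protocol covariates alone: −3.7 (C, N = 78: 56.2 against 59.9) to +4.7 (E, N = 124).
- All three baselines, settings A to D: −0.4 (C, N = 100: 72.7 against 73.1) to +3.5 (D, N = 100: 64.0 against 60.5). In setting E: +4.1 to +5.0.
- Adding eGFR to log 24-hour: −0.8 to +0.9 in A to D, +2.5 to +3.3 in E.
- The raw 24-hour covariate itself beats no adjustment by 2.1 to 7.7.

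Each power has Monte Carlo SE of about √(0.7 × 0.3/1000) = 1.4 points. The models share simulated trials, so differences are tighter, but gaps under about a point should not be read.

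**Log 24-hour plus log FMU, without eGFR.** Four settings with 50 or 62 per arm, 3,000 trials each. Assumed: baseline log SD 0.7–0.8, 24-hour error 0.35–0.45, FMU error 0.25–0.30, log changes −0.92 or −0.7 against −0.22. Raw 24-hour against the two-baseline model:
- 68.6 against 71.1 (+2.5)
- 73.4 against 74.8 (+1.4)
- 45.1 against 47.4 (+2.3)
- 45.9 against 48.6 (+2.7)

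Six further settings gave +0.5 to +2.6 points, with type I error of 4.2% to 5.6%. Another 16 cells for a combined model, with non-prognostic eGFR and spread 0 to 0.4, gave +0.1 to +3.4.

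**Model size.** At the assumed rates and 62 per arm, expected responders are 62 × 0.38 + 62 × 0.17 = 34.1. The SAP model has 5 terms (treatment, baseline, disease type, two strata), about 6.8 responders per term. The proposed model has 6, about 5.7 per term.

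**The case against.** A reader might infer that the SAP gives up precision by leaving the protocol's covariates. The documents do not support that.
- SAP 6.1 says binary models adjust for the baseline of the variable that defines the endpoint. Here that is 24-hour protein, so the SAP's choice is principled.
- The protocol's reference to the composite endpoint's approach can mean logistic regression with composite handling of intercurrent events. Its synopsis calls the 50% uPCR and C3c models similar to the composite model, yet 12.3.2.1 gives each of them its own baseline.
- The protocol covariates alone change sign against the SAP covariate, as shown above. Spread between g/day and uPCR is plausible: g/day is not creatinine-normalised, and body weight at entry can run from 30 to 100 kg.

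A reader might also infer that the tested time point is open. It is not: SAP Table 1 and SAP 6.6.1 both say week 24. The fault is that the other places were not aligned.

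Raw scale and single collection are inferences. SAP 6.6.1 says neither; they follow from its silence where neighbouring sections specify logs, and from the one planned screening 24-hour sample. The sample code does not settle it, because its logistic example is the 50% uPCR endpoint. The addendum's move to logs concerns a continuous outcome, so it is a pointer, not proof, for a logistic covariate.

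Finally, the test counts only if six earlier tests succeed, and the fuller model is specified in neither document. All of this stands. It limits the point to an optional improvement plus a wording repair.

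**Conclusion.** The point holds as a minor improvement. Log 24-hour protein plus baseline log FMU uPCR was about as good as or better than the raw 24-hour covariate throughout, by about 0 to 3 percentage points of power, with type I error near 5%. Baseline eGFR added nothing when not prognostic and a few points when it was. The size rests on assumed baseline spread, measurement errors and non-response; only the log changes and SD come from the documents. In the tabulated runs, disease type and strata were omitted.

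The SAP covariate is not an error. The week 26 wording in Protocol Table 1, Protocol 12.3.2.2 and SAP 2.2.3 is inconsistent with the urine schedule and with SAP 6.6.1, and SAP 15 does not declare the difference in time point or covariates.

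**What to change.** - In SAP 6.6.1, name the baseline as log-transformed screening 24-hour urine protein, add baseline log-transformed FMU uPCR, and keep disease type and the stratification factors. Baseline eGFR may be added. The log is always defined, because entry requires at least 1 g/day on that collection.
- Say which covariate is dropped first if the model fails to converge, since SAP 6.1 allows removal and the expected number of responders is modest.
- State week 24 in Protocol Table 1, Protocol 12.3.2.2 and SAP 2.2.3. List the time point and covariate set in SAP 15.
- SAP Addendum 1 and 11 show the week 26 analysis already reported in the study report of 05 December 2024. In this trial, therefore, the SAP 6.6.1 result stays the formal one, the fuller model is labelled supportive, and the difference from the protocol is discussed in the final report, as Protocol 12 provides.

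Cost: wording, and one or two covariates already in the analysis data.
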